RESEARCH PROTOCOL

TITLE

**Effects of vitamin D₃ supplementation on lung functions and
exercise tolerance in D₃ deficient Asthma COPD Overlap
(ACO) patients**

Date:06/09/2018

Project Summary

Background: Asthma COPD Overlap (ACO) has been described as a distinct disease now-a-days. Several studies have shown positive relationship between serum concentration of 25 hydroxyvitamin D, lung function and exercise tolerance in different group of patients. However, vitamin D supplementation showed significant improvement in lung function status and exercise tolerance in both asthma and COPD patients but no study was found in ACO patients. **Objectives:** To evaluate the effects of vitamin D₃ supplementation on lung function status and exercise tolerance in D₃ deficient, stable patients with ACO. **Methods:** This double blinded placebo controlled trial will be conducted by Department of Physiology Bangabandhu Sheikh Mujib Medical University (BSMMU), Shahbag, Dhaka from March 2018 to February 2019. For this study a total number 70 vitamin D₃ deficient (serum 25 hydroxycholecalceferol <30 ng/ml) male, stable (diagnosed patient, who was not experienced any acute exacerbation, hospitalization, urgent care visits or changes in routine medication within 4 weeks prior to study) patients with ACO of age 40-70 years will be selected. They will be selected from the Out Patient Department (OPD) of the National Institute of Diseases of Chest and Hospital (NIDCH) and will be randomly grouped as A (control) and B (study). All the participants will be matched in terms of age, duration of ACO, duration of smoking, body mass index (BMI), mid upper arm circumference (MUAC), waist hip ratio, occupational status, socioeconomic status, serum

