Is there any improvement in lung function status and exercise tolerance in vitamin D₃ deficient ACO patients after having vitamin D₃ supplementation?

Hypothesis

Null: Vitamin D₃ supplementation does not improve lung functions and exercise tolerance in vitamin D deficient ACO patient.

Alternate: Vitamin D₃ supplementation improves lung functions and exercise tolerance in vitamin D deficient ACO patient.

Objectives:

General objectives:

To evaluate the effects of vitamin D₃ supplementation on lung function status and exercise tolerance in D₃ deficient, stable patients with ACO.

Specific objectives

- To measure the FVC, FEV₁, FEV₆, FEV₁/FVC%, PEFR and FEF_{25-75%} of vitamin D₃ deficient, stable patients with ACO, in order to assess their lung function status at baseline.
- To measure the 6MWD of all the patients, in order to assess their functional exercise capacity at baseline.
- To measure the SpO₂ at rest of all the patients, in order to assess the basal oxygenation status at baseline.
- To measure the level of dyspnea and fatigue at rest of all the patients in order to assess the basal breathlessness level at baseline.
- To measure the both the SpO₂ and level of dyspnea and fatigue again after 6MWT, for the assessment of their exercise tolerance at baseline.
- To measure the all these variables in study group at 13th weeks and at 26th weeks of their follow up.
- To measure the all these variables in control group at 13th weeks and at 26th weeks of their follow up.
- To compare all these variables in study group at baseline and endline.
- To compare all these variables in control group at baseline and endline
- To compare all these variables in both group at baseline and endline.

Methods

Type of study	: Double blinded placebo controlled trial
Place of study	: Department of Physiology, Bangabandhu Sheikh Mujib Medical University (BSMMU), Shahbagh, Dhaka
Period of study	: March 2018 to February 2019
Study population	: Stable patients of ACO with vitamin D ₃ deficiency
Sample size	: 60
Sampling	: Consecutive sampling
Grouping	:
Group A (Control)	: 30 (thirty) D ₃ deficient ACO patients with placebo administration
Group B (Study)	: 30 (thirty) D ₃ deficient ACO patients with vitamin D ₃ administration

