For the assessment of all the variables of all the patients on day 0, at 13th week and as well as at 26th week, they will be designated as A₀, A₁ and A₂ (control) and B₀, B₁ and B₂ (study). In addition, for the mean of SpO₂, level of dyspnea and level of fatigue at resting condition (before 6MWT), all the groups will be further designated as A_{0before}, A_{1before}, A_{2before}, B_{0before}, B_{1before} and B_{2before} respectively. Similarly after 6MWT all these six subgroups will be again designated as A_{0after}, A_{1after}, A_{2after} and B_{0after}, B_{1after}, B_{2after}, for measurement of these three variables.

Sample size calculation

Using the following statistical formula

$$n = [(Z\alpha + Z\beta)^2 \times (\sigma_1^2 + \sigma_2^2)] / (\mu_1 - \mu_2)^2$$

(Kirkwood and Sterne 2003)

$$\text{Mean of control, } \mu_1 = 364.1$$

$$\text{Mean of study group, } \mu_2 = 357.3$$

$$\text{SD of control, } \sigma_1 = 7.21$$

$$\text{SD of study group, } \sigma_2 = 12.25$$

(Hassan 2018)

$$\text{Type I Error, } Z\alpha = 1.96$$

$$\text{Type II Error, } Z\beta = 0.84$$

(Kirkwood and Sterne 2003)

Therefore,

$$\begin{aligned} n &= [(Z\alpha + Z\beta)^2 \times (\sigma_1^2 + \sigma_2^2)] / (\mu_1 - \mu_2)^2 \\ &= [(1.96 + 0.84)^2 \times (7.21^2 + 12.25^2)] / (364.1 - 357.3)^2 \\ &= [7.84 \times (51.9841 + 150.0625)] / (6.8)^2 \\ &= 1584.04534 / 46.24 \\ &= 34.2570359 \\ &= \text{approximately 35 for each group.} \end{aligned}$$

Subject selection:

Inclusion criteria

- Pulmonologist diagnosed stable patient of ACO
(GINA and GOLD 2015)
- Duration of ACO: > 4 year
- Vitamin D₃ deficient : Serum 25(OH)D <30 ng/ml
(Vitamin D Council 2017)
- Age: 40 -70 years
- Sex: Male
- Socioeconomic status: middle class
- Smoker
- Anthropometric status:
 - BMI=18.6-24.9 kg/m²
(WHO 2006)
 - mid upper arm circumference>25.1 cm
(Sultana et al. 2015)
 - waist-hip ratio<0.89
(Sultana et al. 2015)
- Serum parathormone: 10-65 pg/ml
- Serum Ca²⁺: 8.5-10.5 mg/dl
- Serum PO₄³⁻: 2.3-4.7 mg/dl
- Serum alkaline phosphatase: 30-120 U/L
- SGPT: <50 U/L
- Serum creatinine: 0.7-1.3 mg/dl
- FBS: 3.5-6.1 mmol/L
- Serum HbA1c: 4.5-6.3 %

- Serum cholesterol: <200 mg/dl
- Serum HDL: >40 mg/dl,
- Serum LDL: <130 mg/dl
- Serum TG: <150 mg/dl

Exclusion criteria

With history of:

[figure not shown]
- any other pulmonary diseases, as,
 - ✓ chronic obstructive pulmonary disease
 - ✓ bronchial asthma
 - ✓ respiratory tract infection
 - ✓ bronchiectasis
 - ✓ pleural effusion
 - ✓ tuberculosis

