 - ✓ interstitial lung disease
 - ✓ pneumonectomy or pulmonary lobectomy
- any cardiac disease, like –
 - ✓ unstable angina pectoris
 - ✓ congestive heart failure
 - ✓ myocardial infarction
 - ✓ cardiac arrhythmia
- systemic hypertension
- any liver disease
- any malignancy

- use of any drugs known to affect vitamin D metabolism within 1 month prior to study, as,
 - ✓ antiepileptics (Phenytoin, Carbamazepine)
 - ✓ antibiotics (Clotrimazole, Rifampicin)
 - ✓ antihypertensives (Nifedipine, Spironolactone)
 - ✓ antiretroviral drugs (Ritononavir, Saquinavir)
 - ✓ endocrine drugs (Cyproterone acetate)
 - ✓ glucocorticoids
 - ✓ bisphosphonate
 - ✓ calcium supplement

- With biochemical evidence of
 - ✓ diabetes mellitus
 - ✓ renal insufficiency

All the criteria mentioned above will be scrutinized by taking history or clinical examination or laboratory investigations

Study outline:

Site of sample collection

All the patients will be collected from the Out Patient Department (OPD) of National institute of the diseases of chest and hospital (NIDCH), Mohakhali, Dhaka..

Study procedure

On the first day of enrollment, the objectives, nature, purpose and potential risk of all the procedures used for the study will be explained in detail to each ACO patients (diagnosed by pulmonologist), with a cordial attitude giving emphasis on the benefits he might obtain from this study. He will be encouraged for voluntary participation and will be allowed to withdraw himself from the study even after participation, whenever he felt uneasy. If he agreed to be enrolled in the study, an informed written consent will be taken in a prescribed form. Detailed family history, medical history and thorough physical examination of each patient will be done and all the information will be recorded in a standard data sheet. Then all the patients will be requested to attend the Department of Physiology at 7:30 am (after overnight fasting) on the examination day.

On the examination day, 10 ml of venous blood will be collected from antecubital vein of patient in different vacutainer tubes and will be taken to the laboratory of Department of Biochemistry and Molecular Biology . as soon as possible for the estimation of serum creatinine and serum 25(OH)D. and rest of the blood will be preserved at -4°C.

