If the patient with D₃ deficiency [Serum 25(OH)D <30 ng/ml] and not with renal insufficiency (Serum creatinine >1.3 mg/dl), then the Fasting blood sugar, serum HbA_{1c}, serum parathormone (PTH), serum calcium (Ca²⁺), serum phosphate (PO₄³⁻), serum alkaline phosphatase (ALP), serum SGPT, serum cholesterol, serum High Density Lipoprotein (HDL), serum low density lipoprotein (LDL), serum triglyceride (TG), will be assessed from the preserved blood.

After that their height and weight will be measured and the spirometric lung function test will be done by using a portable spirometer (PONY FX, cosmed, Italy]. After getting all the biochemical and spirometric reports the final selection will be done, according to the inclusion and exclusion criteria. All the eligible patients will be randomly assigned to either 'Control' or 'Study' groups and will be thoroughly informed about the objectives and detailed study procedure, once again.

Subsequently a standard therapeutic treatment (according to GOLD guideline) will be prescribed to all the selected stable ACO patients of both groups. Proper education will be given about drug, method of taking medication and medication plan.

Along with the standard pharmacological treatment of ACO, the patients of the 'Study group' will be prescribed for 80,000 IU/ week of oral vitamin D₃, for consecutive 13 weeks. Subsequently, all the patients will be cordially requested to again visit the Department of physiology, BSMMU, on 13th week of their follow up to reexamine all the study

variables along with serum 25(OH)D and Ca^{2+} (to check the toxicity). These data will be recorded as values of '13th week' (B13).

Then according to serum level of 25(OH)D and Ca^{2+} (American Vitamin D council 2017), 40,000 IU / 1 to 6 week oral vitamin D₃ will be prescribed, for further 13 weeks. At 26th week of follow up, they will be requested again to visit the Department of Physiology, BSMMU, to reexamine all the study variables, and the data will be recorded as values of '26th week' (B26).

Similarly, all the patients of 'control group' will be prescribed for placebo (along with standard pharmacological treatment of ACO, prescribed by pulmonologist) for consecutive 26 weeks and their respective data will be recorded as A13 and A26.

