fatigue(score)

Haematological variables:

Variables	On day 1	On day 90	On day 180
Serum 25(OH)D (mg/ml)			
Serum Ca ² (mg/dl)			
Serum PO ₄ ³⁻ (mg/ml)			
Serum PTH (pg/ml)			
Serum creatinine(mg/dl)			
Serum SGPT (U/L)			
Serum cholesterol (mg/dl)			
Serum TG (mg/dl)			
Serum HDL (mg/dl)			
Serum LDL(mg/dl)			
Serum FBS (mmol/L)			
Serum HbA1c (%)			

Modified borg scale:

SCALE	SEVERITY
0	No Breathlessness At All
0.5	Very Very Slight (Just Noticeable)
1	Very Slight
2	Slight Breathlessness
3	Moderate
4	Somewhat severe
5	Severe Breathlessness
6	
7	Very Severe Breathlessness
8	
9	Very Very Severe (Almost Maximum)
10	Maximum

AppendixIII

Standard pharmacotherapy for stable patient of ACO:

(GOLD 2015)

- **Inhaled corticosteroid** (in low or moderate dose, depending on level of symptoms)
- **Inhaled long acting bronchial agonist (LABA), and /or**
- **long acting muscarinic agonist (LAMA)**
- **Advice-**
 - on smoking cessation.
 - Appropriate self management strategies.
 - Regular follow up.

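### The glucocorticoid exclusion states no route, although Appendix III makes inhaled corticosteroid standard therapy for the same patients: a minor wording conflict that affects recruitment and the within-arm tests, not the randomised comparison

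*Combined protocol and SAP*

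**What the plan says.** - **Exclusion criteria.** The plan excludes "use of any drugs known to affect vitamin D metabolism within 1 month prior to study". The drug list beneath includes "glucocorticoids", with no route, dose or duration. The Project Summary repeats the exclusion in general terms and makes no exception for inhaled drugs.
- **Appendix III.** Under "Standard pharmacotherapy for stable patient of ACO", the first item is inhaled corticosteroid, "in low or moderate dose, depending on level of symptoms". The and/or wording belongs to the long-acting bronchodilators (LABA, LAMA), not to the steroid.
- **Study procedure.** After baseline spirometry, final selection and random assignment, the plan states: "Subsequently a standard therapeutic treatment (according to GOLD guideline) will be prescribed to all the selected stable ACO patients of both groups". Vitamin D₃ or placebo is given alongside.
- **Who the patients are.** Inclusion requires "Duration of ACO: > 4 year". The stability definition in the Project Summary rules out "changes in routine medication within 4 weeks prior to study".
- **Analysis.** The Specific objectives ask for a baseline-to-endline comparison within each arm and a comparison of the two arms. The Statistical Analysis section assigns paired t tests to the first and the independent-sample t test to the second, and does not say which carries the conclusion.

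**The concern.** The eligibility rule and the background treatment do not fit together. A patient with several years of diagnosed ACO who is already on the regimen that the protocol calls standard has used a glucocorticoid in the past month and, on the words as written, is excluded. A patient who does qualify has had no glucocorticoid for a month and is then prescribed ICS on the same day as the study drug.

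Two things are at stake. The first is recruitment and generalisability: the trial would describe vitamin D added to newly started ICS, not to established therapy. The second is the pair of within-arm tests. The history form in Appendix II itself lists a response to ICS over weeks among the features that favour asthma, so a steroid start after baseline could move spirometry in both arms during the 26 weeks. A significant before-and-after change in the vitamin D arm could then be credited to vitamin D.

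**Working it through.** The plan gives no figure on this point, so the texts are compared first. Two illustrations under assumed inputs follow.

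**1. The texts side by side**

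- The exclusion covers the whole drug class for 1 month before the study. No limit to systemic use appears in the text available for review.
- Appendix III places ICS in standard therapy for the stable patient.
- On the literal reading, a patient on ICS is therefore excluded. To enter, he would have to stop. The stability rule then keeps him out for 4 weeks and the exclusion for a month. No washout is planned.
- Everyone who does enter has been free of glucocorticoid for a month, so for him the treatment prescribed after randomisation is a new start or a restart.
- On a systemic-only reading, none of this follows.

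**2. Recruitment (assumed share on ICS)**

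Inputs: the study period is "March 2018 to February 2019" (Methods), about 52 weeks. Follow-up takes 26 weeks, so enrolment has about 52 − 26 = 26 weeks. The target N is 60 in Methods and 70 in the Project Summary. The share q of otherwise eligible patients on ICS is not in the documents.

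Otherwise eligible patients needed = N / (1 − q); weekly rate = that number / 26.

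| Assumed q | N = 60: needed (per week) | N = 70: needed (per week) |
|---|---|---|
| 0% | 60 (2.3) | 70 (2.7) |
| 25% | 80 (3.1) | 94 (3.6) |
| 50% | 120 (4.6) | 140 (5.4) |
| 75% | 240 (9.2) | 280 (10.8) |
| 90% | 600 (23) | 700 (27) |

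Under a systemic-only reading the first row applies whatever the share.

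**3. Paired tests (assumed shared change, no vitamin D effect)**

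Let d be the mean change common to both arms divided by the SD of change. The paired t test at two-sided 0.05 has n − 1 degrees of freedom and non-centrality d√n. Let p be the probability of a significant improvement in one arm. The arms are independent, so the probability of significance in the vitamin D arm only is p(1 − p), and the same holds for the placebo arm only.

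Example: n = 30 and d = 0.25 give non-centrality 0.25 × √30 = 1.37 and critical value 2.045. Hence p = 0.262 and p(1 − p) = 0.194.

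| d | n = 30: p | n = 30: one named arm only | n = 35: p | n = 35: one named arm only |
|---|---|---|---|---|
| 0 | 0.025 | 0.024 | 0.025 | 0.024 |
| 0.125 | 0.097 | 0.088 | 0.107 | 0.096 |
| 0.25 | 0.262 | 0.194 | 0.301 | 0.210 |
| 0.375 | 0.510 | 0.250 | 0.578 | 0.244 |
| 0.5 | 0.754 | 0.186 | 0.820 | 0.148 |

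The value of d is assumed and is not tied to ICS. Any change common to both arms gives the same table.

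**4. Between-arm test**

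A shift that is the same in both arms adds the same constant to both means and cancels in their difference. In a simulation of 100,000 trials per setting, the between-arm t test on change rejected in 5.0% to 5.1% at d = 0, 0.125, 0.25 and 0.5, for both n = 30 and n = 35. The plan does not say whether the independent t test uses change or week-26 values. The cancellation holds for either.

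**The case against.** The strongest reply is that the sponsor meant systemic steroids. The patients have long-standing disease under a pulmonologist, are on unchanged routine medication, and belong to a group for which the protocol calls ICS standard. Most of the other drugs in the list are taken systemically. On that reading one word is missing and nothing else is wrong. This stands as a plausible intent, and it keeps the point minor. It does not settle the matter, because screeners apply the written rule, and the data form records earlier drugs only as free text.

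A second reply is that the Study procedure speaks of prescribing treatment without saying whether it is started or continued. That is fair. The new start follows only when the exclusion is applied literally.

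A third reply is that neither table measures this defect. That also stands. The recruitment range includes no effect at all, and the documents give no clinic throughput against which to judge a rate. The paired-test figures would follow equally from the LABA/LAMA prescribed at the same time, the sunlight advice, the medication education or the smoking-cessation advice.

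A reader might go further and infer that the vitamin D comparison is biased. The documents do not support this: both randomised arms receive the same background therapy and advice. The Introduction links higher vitamin D levels to a better glucocorticoid response. If that holds, the between-arm result would describe vitamin D on top of newly started ICS, which limits generalisability but is not bias.

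**Conclusion.** The conflict is in the text and should be corrected, but it is minor. Under the literal reading the rule excludes patients on the protocol's own standard therapy and makes ICS a post-baseline change in those who enter. The harm falls on recruitment, on generalisability and on the interpretation of the within-arm paired tests. The between-arm comparison keeps its validity.

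The size is not known. It depends on how the exclusion is applied, on the share of otherwise eligible patients using ICS, and on how far outcomes shift in both arms together; the documents give none of these. The figures above show what would follow under stated assumptions and are not specific to ICS. A reader might infer that the trial cannot recruit, or that the paired tests would be sound once the exclusion is reworded. Neither follows: no recruitment rate is documented, and the paired tests would still absorb every other change that the arms share.

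**What to change.** 1. Reword the exclusion to systemic glucocorticoids within 1 month. State that ICS is permitted if the regimen has been unchanged for at least 4 weeks before baseline, in line with the stability definition, and that it is continued unchanged where possible. Patients not yet on standard therapy would still start it after baseline unless they are stabilised on it first, so this reduces the within-arm confounding without removing it.
2. Add one sentence saying that the vitamin D conclusion rests on the planned between-arm independent t test at week 26 and that the paired tests are descriptive.

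The cost is one amended criterion and one sentence, with no new analysis and no larger sample. The downside is that any effect of ICS on vitamin D metabolism is accepted. Appendix III already accepts it in both arms, and serum 25(OH)D is measured again at weeks 13 and 26. The protocol is dated 06/09/2018, within a study period that began in March 2018, so enrolment may already have begun. If so, record the rewording as a dated amendment, so that patients screened under each wording can be told apart.

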25hydroxycholecalciferol [25(OH)D], serum parathormone (PTH) , serum calcium (Ca^{2+}), serum phosphate (PO_4^{3-}) ,serum alkaline phosphatase (ALP), serum glutamate pyruvate transaminase (SGPT), serum creatinine, fasting blood sugar (FBS), serum glycated haemoglobin ($\text{HbA}_{1\text{C}}$), serum cholesterol, serum high density lipoprotein (HDL), serum low density lipoprotein (LDL), serum triglyceride (TG). Any patient with history of any acute exacerbation of any pulmonary, liver, endocrine or renal disease, or with any malignancy or with any drug known to affect vitamin D metabolism within 1 month prior to study, will be excluded from the study. All the baseline data at day 0 will be recorded as A0 (Control) and B0 (Study). Along with the standard pharmacological treatment of ACO (according to GOLD criteria), the patients of the ‘Study group’ will be prescribed for 80,000 IU of oral vitamin D_3 per week and ‘Control group’ for placebo for consecutive 13 weeks. Subsequently, all the patients will be cordially requested to again visit the Department of physiology, BSMMU, on 13th week of their follow up to reexamine all the spirometric variables along with serum 25(OH)D and Ca^{2+} (to check the toxicity). These data will be recorded as values of ‘13th week’ (B_1). Then according to serum level of 25(OH)D and Ca^{2+} (American Vita min D council 2017), 40,000 IU / 1 to 6 week oral vitamin D_3 will be prescribed, for further 13 weeks. At 26th week of follow up, all the study variables will be again reexamined, and the data will be recorded as values of ‘26th week’ (B_2). Similarly, all the patients of ‘control group’ will be prescribed for placebo (along with standard pharmacological treatment of ACO, prescribed by pulmonologist) for consecutive 26 weeks and their respective data will be recorded as A_1 and A_2 . With this, all patients of both the groups were

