With these, all patients of both the groups will be advised to continue ad lib (according to their own choice) diet as well as to have sunlight exposure (within 10 am to 2 pm) only for 20 minutes daily (Manjeeta 2016).

In the mean time, a good rapport will be built up to take time to time follow-up over telephone and visiting patient's place with scheduled appointment to maintain a proper follow up at 1st (day 1) 2nd (at 13th week) and 3rd (at 26th week) visit of the study , in addition to the hematological values.

Any patient, who will be failed to follow the study procedure exactly during study period, will be dropped and a new one will be included to fulfill the desired total sample number.

Test procedure for spirometry

(Hassan 2018)

- At first, the subject will be asked to take rest sitting on a chair and remain calm and quiet for 5 minutes.
- The detailed procedure will be explained to him to ensure his maximum cooperation.
- The switch of spirometer will be on and windows will be open.
- Patients' information will be filled up and saved.
- The patient will be asked to hold a disposable paper mouthpiece (connected to spirometer) in his hand horizontally and to place it in between his two lips.
- To make good seal, he will also be asked to put the lips tightly around the outside of the mouthpiece.
- Then he will be asked to inhale first as deeply and as rapidly, as possible, which was followed by a forceful expiration for the possible longest period into the mouthpiece.
- The readings of different variables will be recorded from the spirometer monitor.
- Three (3) consecutive readings at 5 minutes interval for each parameter will be taken and the best value will be noted.

Test procedure for pulse oximetry

(Hassan 2018)

- The patient will be asked to take rest and remain calm and quiet for 10 minutes (MacAllister et al. 2007).
- The detailed procedure will be explained to him to ensure his maximum cooperation.
- Then his right index finger will be washed with alcohol and pulse oximeter sensor will be applied.
- The switch button will be on.
- The reading will be recorded from the display screen.
- Three (3) consecutive readings at 5 minutes interval will be taken and the best value will be noted.

Procedure for six minute walk test (6MWT)

(Hassan 2018)

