Appendix IV

Cholecalciferol supplementation schedule for D₃ deficient [serum 25(OH)D<30 ng/ml] ACO pts

Our aim is

- to avail (within 6 months) and maintain serum 25(OH)D @ 60-80 ng/ml + serum Ca²⁺ @ 8.5-10.5 mg/ml,
- for having extra-calcaemic effect of vitamin D₃,
- on lungs and other tissues

At 1st visit / at day 0:

Cholecalciferol 80,000 IU (2 capsules of 40,000 IU) / wk, for 12 weeks (3 months)

At 2nd visit / at day 90 / after 3 months:

If, serum 25 (OH)D + serum Ca ²⁺ =	Then, for next 3 months, prescribed dose will be -	So, for next 3 months, dose schedule will be -
30-40 ng/ml + 8.5-10.5 mg/ml	4600 IU/day	4600 IU X 7 = 32,200 IU / 7 days = 1 cap (40,000 IU) / wk
40-50 ng/ml + 8.5-10.5 mg/ml	3000 IU/day	3000 X 15 = 45,000 IU / 15 days = 1 cap (40,000 IU) / 2 wks
60-80 ng/ml + 8.5-10.5 mg/ml	not suggested in guideline, but, to get extra-calcaemic effect of D₃	1 cap (40,000 IU) / 6 wks
> 80 ng/ml + 8.5-10.5 mg/ml	stop taking drug & symptom analysis	no dose for 3 months
>150 ng/ml + >10.5 mg/ml	close monitoring and ask for – 
 • feeling sick or being sick • poor appetite or loss of appetite • feeling very thirsty • passing urine often 	no dose for 3 months

	
• constipation or diarrhea• abdominal pain• muscle weakness• pain• bone pain• feeling confused• feeling tired	
--	---	--

At 3rd visit / at day 180 / after 6 months:

Pt will be referred to physician and will be suggested to follow the above-mentioned schedule

Ref: Vitamin D Council. I tested my vitamin D level. What do my results mean? 2017 [Internet]. [Cited 2018 March 25]. Available from: <https://www.vitamindcouncil.org/i-tested-my-vitamin-d-level-what-do-my-results-mean/>

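### In the visible text, no toxicity question or dosing decision is tied to the 80,000 IU/week phase before week 13, and the drop-and-replace rule has no exception for a safety hold

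*Combined protocol and SAP*

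**What the plan says.** Study procedure gives the first-phase dose as "prescribed for 80,000 IU/ week of oral vitamin D₃, for consecutive 13 weeks". Appendix IV gives the same weekly dose for a slightly shorter course: "Cholecalciferol 80,000 IU (2 capsules of 40,000 IU) / wk, for 12 weeks (3 months".

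The first post-baseline safety bloods come at the week-13 visit, when the plan re-examines "variables along with serum 25(OH)D and Ca^{2+} (to check the toxicity"). The Project Summary puts the check at the same time. The result then sets the second phase, in which "40,000 IU / 1 to 6 week oral vitamin D₃ will be prescribed, for further 13 weeks". The Appendix IV rows for stopping the drug and asking about symptoms stand under the day-90 visit and govern the three months after it. The blood table in Appendix-II has columns for days 1, 90 and 180 only.

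Between visits, Study procedure plans "time to time follow-up over telephone and visiting patient's place with scheduled appointment". The purpose it gives is "to maintain a proper follow up at 1st (day 1) 2nd (at 13th week) and 3rd (at 26th week) visit of the study". No interval, symptom question or action is attached.

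The same section says that a patient who "failed to follow the study procedure exactly during study period, will be dropped and a new one will be included". It does not mention doses held for safety. The visible Statistical Analysis text names tests (t tests, one-way ANOVA, Pearson correlation) and has no rule on analysing patients in the group to which they were randomised.

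**The concern.** Two gaps meet in the first phase.

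The first is about safety. The sponsor judged a toxicity check, a stop rule and a symptom list to be needed, but as placed they can change only what is taken after day 90. If a patient develops symptoms in week 5, the visible text does not say that anyone will ask, or who decides whether he takes the next capsules.

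The second is about bias. If his capsules are held, he no longer follows the weekly schedule exactly. Read literally, the rule then removes him and puts a new patient in his place. His week-13 and week-26 values would be lost, and his week-13 calcium and 25(OH)D would never be measured. Patients removed this way would be selected by how they tolerated treatment, so both the efficacy comparison and the toxicity data would lean towards those who tolerated it.

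**Working it through.** The plan states no cumulative dose or expected toxicity rate, so there is no figure of its own to reproduce on this point.

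**Inputs**
- Weekly dose 80,000 IU; 13 weeks (Study procedure) or 12 weeks (Appendix IV).
- Toxic dose cited in Rationale: 50,000 IU/day for several months.
- Second phase: from 40,000 IU weekly down to 40,000 IU every 6 weeks, or nothing (Appendix IV).
- Arm size: 30 (Methods) or 35 (Sample size calculation).

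**Dose taken before the first scheduled check**
- 80,000 × 12 = 960,000 IU.
- 80,000 × 13 = 1,040,000 IU.

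**Daily equivalent against the cited toxic dose**
- 80,000 / 7 = 11,429 IU/day.
- 11,429 / 50,000 = 22.9%. The cited toxic dose is about 4.4 times higher (50,000 × 7 / 80,000 = 4.375).

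**Share of all study vitamin D given in the first phase, if the second phase runs at its highest dose**
- The second phase is then 40,000 × 12 = 480,000 IU or 40,000 × 13 = 520,000 IU.
- Lowest share: 960,000 / (960,000 + 520,000) = 64.9%.
- Highest share: 1,040,000 / (1,040,000 + 480,000) = 68.4%.
- The share is larger at any lower second-phase dose. It describes exposure, not risk.

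**What stands before week 13, side by side**
- Blood tests: none after baseline.
- Stop rules and symptom list: Appendix IV, day 90 only.
- Contacts: planned, with no toxicity content stated.
- Withdrawal: Study procedure lets a patient leave the study at any time, but this is an exit and not a dose pause.
- Other cover: Appendix III advises regular follow-up in standard care, and Appendix-V makes a qualified physician responsible for medical care. Neither says what to do with the study capsules.

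**Replacement rule**
- It contains no safety exception. The walk-test procedure points the same way: a test stopped for symptoms also leads to the subject being dropped.
- The issue applies before day 90 only, because a stop from day 90 onwards is itself part of the Appendix IV schedule.
- One replaced patient is 1/35 = 2.9% to 1/30 = 3.3% of an arm.

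**What a question at the contacts would change**
- With contacts at about weeks 4, 8 and 12, the first stated question comes after about 4 doses: 4 × 80,000 = 320,000 IU, which is 4/13 = 31% to 4/12 = 33% of the course.

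**The case against.** The strongest reply is that the risk is low and the gap may be only on paper. Entry requires 25(OH)D below 30 ng/ml with normal calcium, parathormone and creatinine, and calcium supplements and renal insufficiency are excluded. Rationale also cites 10,000 IU/day (70,000 IU/week), close to the study dose, though for only 4 weeks. This stands, and it is why the point is not a claim of harm.

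Pages are also missing from the public copy, including the consent pages, and the visible appendices begin at the second. Advice to patients could well sit there. Study procedure says that risks will be explained, and the sentence on contacts goes on to mention blood values in wording that is hard to interpret. So the finding can be only about the visible text.

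On replacement, a hold ordered by a physician is not naturally a patient's failure to comply, and an investigator might never apply the rule to it. That is fair: the literal reading is arguable and not certain. Safety holds are also a small, possibly empty, part of the wider problem of replacing randomised patients for any departure.

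Three stronger readings are tempting and not supported:
- A reader might infer from the large share of dose given before any stop rule that patients face material risk. The shares restate a load-then-adjust schedule, and the documents give no toxicity rate.
- A reader might infer that the top row of Appendix IV shows that toxicity was expected. The ladder is credited to a general guideline and is reused after the trial.
- A reader might infer that the final comparison would describe only those who tolerated the course. With an unknown and probably small number of holds, the documents do not support a distortion of that size.

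**Conclusion.** The point holds in limited form. In the visible text, 12 to 13 weekly doses (960,000 to 1,040,000 IU) are taken before any stated toxicity question or dosing decision, at about 23% of the daily dose the plan itself calls toxic. This is an omission worth correcting because correction is cheap; no hazard has been shown, and expected cases cannot be calculated.

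The replacement rule is the part with a statistical consequence. Read literally, it takes a safety-held patient out of his randomised group and out of the week-13 toxicity test. The size is 2.9% to 3.3% of an arm per patient, multiplied by a number that is unknown and probably small.

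The conclusion assumes that the missing pages contain neither a symptom-reporting step nor a safety exception. If they do, the matching part falls away. It should be corrected, with medium confidence.

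**What to change.** Amend Study procedure in two places.

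1. **Replacement rule.** State that a patient whose capsules are held or stopped for safety is not dropped or replaced, attends weeks 13 and 26, and is analysed in his randomised group. Make the 13-week course subject to such a hold.
2. **Contacts in weeks 1 to 13.** Give the existing telephone and home contacts an interval, for example about every 4 weeks. Ask both arms the Appendix IV symptom list in identical words, and record the answer and date. Refer new or clearly worse symptoms to the treating pulmonologist, who decides on holding the capsules (active or placebo) and on any calcium check. A single non-specific symptom should not trigger an automatic hold. If the missing pages already advise patients on symptoms, use the same wording.

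No new committee, clinic visit or scheduled blood test is needed. The cost is a short amendment and one line per contact on the data form. Three contacts for 60 to 70 patients is 180 to 210 contacts; at an assumed 3 to 10 minutes each, that is 180 × 3 min = 9 hours to 210 × 10 min = 35 hours over the trial. Time for referrals and any calcium checks is extra and not estimated.

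The downside is some referrals and short holds in both arms for symptoms such as tiredness and weakness, which overlap with the lung disease. The first scheduled laboratory check stays at week 13, so symptom-free hypercalcaemia would still not be found earlier.
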